9.8 Definition of On-treatment Period

The on-treatment period is defined as the time from the first study intervention administration to the last study intervention administration date + 30 days or the earliest date of subsequent anticancer drug therapy minus 1 day, whichever occurs first, unless otherwise stated.

For participants with treatment ongoing at cut-off date, all data from the first study intervention up to the cut-off date will be considered under the on-treatment period.

Any systemic anticancer therapy, any anticancer surgery and any anticancer radiotherapy as documented in the “Anti-cancer treatment after discontinuation details”, “Radiotherapy after discontinuation details” and “Surgery after discontinuation details” eCRF pages will be considered as subsequent anticancer therapy.

The on-treatment period will include the initial treatment period as well as the reinitiation of treatment period, as applicable. Whether the participant reinitiates treatment (following the rules as outlined in the protocol) or not, the on-treatment period is defined as the time from the first study intervention administration to the last study intervention administration date + 30 days or the earliest date of subsequent anticancer drug (anticancer therapy, anticancer surgery and anticancer radiotherapy) therapy minus 1 day, whichever occurs first, unless otherwise stated.

For immune-related AEs as listed in Section 15.2.3.2, an expanded on-treatment period will be used as a default for any analysis: time from the first trial drug administration to the last trial drug administration date + 90 days, death OR to the earliest date of subsequent anticancer therapy minus 1 day, whichever occurs first, unless otherwise stated.

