Dates of study treatment	
Start date of study treatments:
 
 No imputation will be done. 
End date of study treatments:
 
In case the last date of study drug is missing or incomplete the date of last administration of study drug will be taken from the treatment termination eCRF pages.
 
 If the last date of study drug is completely missing and there is no End of Treatment eCRF page and no death date the participant should be considered to be ongoing and use the cut-off date for the analysis as the last dosing date If the last date of study drug is completely or partially missing and there is EITHER an End of Treatment eCRF page OR a death date available (within the cut-off date) then imputed last dose date is: 
 = 31DECYYYY, if only Year is available and Year < Year of min (EOT date, death date) = Last day of the month, if both Year and Month are available and Year = Year of min (EOT date, death date) and Month < the month of min (EOT date, death date) = min (EOT date, death date), for all other case
Death date	
For the purpose of survival analyses (PFS and OS) partially missing death dates will be imputed as follows:
 
If only the day is missing, the death date will be imputed to the maximum of the (non-imputed) day after the date of last contact and the 15th day of the month.
 
Otherwise it will not be imputed.
 
In listings, the imputed date of death will be presented with a flag indicating the level of imputation.

CCI

CCI

CCI

CCI

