$$\text{Duration of treatment} = \left(\frac{\text{date of last dose} - \text{date of first dose} + 14}{7} \right)$$

The **cumulative dose** overall of bintrafusp alfa per participant is the sum of the actual dose that the participants received during the study (i.e., total dose administered (mg)).

The **dose intensity** of treatment (DI) (mg/cycle) of bintrafusp alfa during the study is defined as

$$\text{DI of treatment} = \left(\frac{\text{Cumulative dose of treatment (mg)}}{\text{Duration of bintrafusp alfa of treatment (in weeks)/2}} \right)$$

The **relative dose intensity** (RDI) is defined as the actual dose intensity divided by the planned dose intensity during the study and expressed in percentage:

$$\text{RDI of treatment (\%)} = 100 \times \left(\frac{\text{DI of treatment (mg/cycle)}}{\text{planned dose (mg/cycle)}} \right)$$

Where the planned dose is 1200 mg/cycle

The following summary tables will be provided:

- Duration of therapy (weeks)
- Total number of infusions received
- Cumulative dose (mg)
- Dose intensity (mg/week)
- Relative dose intensity (%) as continue variable, and categorized as
 - < 80%
 - 80%-90%
 - > 90%

Duration of therapy and cumulative dose, dose intensity and relative dose intensity tables may be repeated by Japanese status (Japanese, non-Japanese, all).

Two listings will be presented:

- A listing of study intervention which will provide: participant identifier, age, sex, race, visit, infusion start date and time, infusion end date and time, infusion rate (mL/hr), actual dose (mg), route, administration modification and reason for modification, change in administration detail, treatment delay (days). Data collected during the treatment reinitiation phase will be flagged.
- An additional listing of treatment exposure and compliance which will include participant identifier, age, sex, race, duration of therapy (weeks), total number of infusions received, cumulative dose of therapy (mg), dose intensity (mg/week), and relative dose intensity (%).

Dose Modification

Dose modification is not allowed per protocol. No summaries will be provided.

Therapy Delays

Delays of therapy will be derived for each infusion as the number of days since last infusion – 14:

Therapy Delays = start date of current infusion – start date of the previous infusion – 14

If the result is > 0 day, then this will be classed as a delay. A participant may have more than one treatment delay throughout the course of treatment.

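### SAP 9.9 has no branch for a last dose with known month, missing day and an end-of-treatment or death date in a later calendar year, so it is dated after its known month

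*SAP*

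**What the plan says.** The rule is in the row on dates of study treatment in SAP 9.9. It works in steps.

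- **First source.** Before anything is imputed, a gap in the last-dose date is filled from another form: "the date of last administration of study drug will be taken from the treatment termination eCRF pages".
- **When the imputation branches apply.** The trigger opens as follows: "If the last date of study drug is completely or partially missing and there is EITHER an End of Treatment eCRF page OR a death"; whichever of the two exists must fall within the cut-off.
- **Branch 1, year only.** "31DECYYYY, if only Year is available and Year < Year of min (EOT date, death date".
- **Branch 2, year and month.** Month end is used on this condition: "if both Year and Month are available and Year = Year of min (EOT date, death date) and Month < the month of min".
- **Branch 3, catch-all.** "min (EOT date, death date), for all other case".

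The resulting date is used in several places. SAP 13 computes treatment duration in weeks as last dose minus first dose plus 14 days, divided by 7, and duration is the denominator of dose intensity and RDI. SAP 9.8 ends the on-treatment period at "the last study intervention administration date + 30 days or the earliest date of subsequent anticancer drug therapy minus 1 day, whichever occurs first", and uses 90 days in place of 30 for immune-related events. SAP 15.2.1 counts deaths within 30 days of last dose. Exposure, treatment-emergent events, events of special interest and deaths all remain in the restricted analysis of SAP 6.1.

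**The concern.** Branch 1 needs the month to be unknown. Branch 2 needs the known year to equal the year of min(EOT, death). A last dose known to fall in, say, November 2020 with EOT in February 2021 meets neither condition and goes to the catch-all, which dates it in February 2021. Nothing in the rule caps the imputed date at the end of the known month.

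Three features show that this is a slip and not a deliberately conservative choice. The imputed date contradicts recorded data. More information gives a worse answer: the year alone yields 31 December 2020, while year and month yield a date in 2021. And the same gap inside one calendar year is handled properly. The neighbouring rules in SAP 9.9 for adverse event stop dates and medication end dates also use month end when only the day is missing, limited only by the date of death and with no condition on the year.

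For an affected participant the stake is a wrong treatment duration and RDI, a safety window that may be too long, and a death that may be counted in the wrong category.

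**Working it through.** The documents state no figure on this point, so there is none to reproduce. The check applies the three branches literally to assumed dates. In every case the termination page is also assumed to give no complete date.

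**Branch logic** (ref = the earlier of EOT and death)

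| Known part of last dose | ref | As written | Month-end rule | Excess |
|---|---|---|---|---|
| 2020 only | 10 Jan 2021 | 31 Dec 2020 (branch 1) | 31 Dec 2020 | 0 days |
| Dec 2020 | 10 Jan 2021 | 10 Jan 2021 (branch 3) | 31 Dec 2020 | 10 days |
| Nov 2020 | 10 Jan 2021 | 10 Jan 2021 (branch 3) | 30 Nov 2020 | 41 days |
| Oct 2020 | death 15 Jun 2021, no EOT page | 15 Jun 2021 (branch 3) | 31 Oct 2020 | 227 days |
| Mar 2021 | 15 May 2021 | 31 Mar 2021 (branch 2) | 31 Mar 2021 | 0 days |

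In the fourth row the last dose becomes the date of death, so the death is automatically counted as within 30 days of last dose.

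**Exposure example.** Assumed: 6 infusions of 1200 mg every 2 weeks, first on 11 September 2020, last on 20 November 2020 with the day missing, EOT 5 February 2021.

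- Duration = (last − first + 14)/7.
  - True date: (70 + 14)/7 = 12.0 weeks.
  - Month end, 30 November: (80 + 14)/7 = 13.4 weeks.
  - As written, 5 February: (147 + 14)/7 = 23.0 weeks.
- RDI = 100 × [6 × 1200/(duration/2)]/1200 = 100 × 12/duration: 100% (true), 89.4% (month end), 52.2% (as written).
- Cumulative dose is 6 × 1200 = 7200 mg and the number of infusions is 6 in all three cases.
- Excess over the month-end rule: 5 February 2021 − 30 November 2020 = 67 days.
- With no subsequent anticancer therapy, the 30-day window ends on 7 March 2021 instead of 30 December 2020. The 90-day window ends on 6 May 2021 instead of 28 February 2021 (assuming no earlier death). Each moves by 67 days.

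**Dependence on the gap between last dose and ref.** A day-missing last dose was placed on each day of a 365-day year, with an assumed fixed gap.

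| Assumed gap | Share of day-missing dates hitting the fault | Mean excess over month end |
|---|---|---|
| 14 days | 14/365 = 3.8% | 7.5 days |
| 28 days | 28/365 = 7.7% | 14.5 days |
| 60 days | 60/365 = 16.4% | 45.5 days |
| 90 days | 90/365 = 24.7% | 75.5 days |

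These are shares of incomplete dates that the termination page does not complete, not shares of participants.

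**Can a year end fall in the treatment period?** SAP 6.1 sets the cut-off at 15 February 2022. Protocol 9.4.4 places the primary analysis 12 months after the last planned global participant was accrued. If the cut-off follows that timing, accrual ended around mid-February 2021, and both the 2020/21 and 2021/22 year ends lie in the period when participants could be on treatment.

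**The case against.** The strongest objection is rarity. The rule looks first to the treatment termination page, and a participant with an EOT date would normally have one that supplies the last administration date. Infusions are given at the site and their date, time and dose are entered in the eCRF (Protocol 6.4). A data review meeting precedes any database lock (SAP 6), and imputed values are flagged in listings (SAP 9.9), so an affected record would be visible. All of this stands and limits the size of the point. It does not remove the fault, because the branches exist for exactly the dates that remain incomplete after those steps.

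The long gap in the example can also be challenged. Dosing is every 2 weeks and the end-of-intervention visit falls on, or within 7 days of, the decision to discontinue (Protocol Table 1), so short gaps may be usual and the excess is then about one to two weeks. Longer gaps are possible, since that visit is tied to the decision and not to the last dose. A reader might take the 12-week limits in Protocol 6.8 as permission to hold drug for that long. They are criteria for permanent discontinuation, and long holds are only an inference from them.

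Three stronger readings are tempting, and the documents do not support them.

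- That the last dose is moved whenever treatment ends after New Year. A complete date from either source is left alone.
- That exposure as a whole is overstated. Only duration is. Cumulative dose and number of infusions do not use this date (SAP 13), and RDI moves down.
- That the example error is 77 days. That is the distance from the true date of 20 November, which no imputation rule can know. The part due to the faulty branch is 67 days.

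Finally, both safety windows still stop the day before subsequent anticancer therapy, so they may lengthen by less than the date error.

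**Conclusion.** The branch is wrong as written, and nothing elsewhere in either document closes the gap. It acts only when four conditions hold together: the day is missing; the month and year are known; the termination page gives no complete date; and min(EOT, death) falls in a later calendar year. For such a participant the error can be large, 67 days in the assumed example, with duration 23.0 against 13.4 weeks and RDI 52% against 89%. Across the trial it is likely to be small, because few participants should meet all four conditions; the documents give no count. Confirmed objective response does not use the last-dose date, so the primary endpoint is unaffected. This is a minor specification error worth correcting because the correction is simple and certain.

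**What to change.** Reword branch 2 of the last-dose rule in SAP 9.9 so that it gives the last day of the known month when year and month are available and either the year is before the year of min(EOT, death), or the year is the same and the month is earlier. Keep the termination-page step and the other branches. Results for same-year cases do not change.

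The cost is one clause in the SAP and one condition in the program, with no new data and no effect on conduct. If outputs have already been run, a search of the flagged imputed last-dose dates will show whether any participant is affected.

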9.11 Other Derivations

Data collected after reinitiated treatment	Data collected after reinitiation of treatment will be included in the summary statistics. A data listing will include AE data for all reinitiated patients.
Re-screened participants	Re-screened participants will be only counted once in the screening analysis set, considering the latest screening (screening with latest informed consent).
Preferred term for analysis of WHO-DD coded data	For data coded according to WHO Drug B3 (e.g., concomitant medications), summaries will be done on the preferred term level where the preferred term is corresponding to codes ending in CCI. With this approach, variations of salt forms of active ingredients will be analyzed under the same term, e.g. diphenhydramine and diphenhydramine hydrochloride will be analyzed as the same preferred term diphenhydramine.
Unscheduled assessments	
As per database definition, the safety unscheduled assessments are always linked to a scheduled timepoint (each unscheduled assessment is linked to the previous scheduled timepoint). Safety data retrieved from an unscheduled timepoint (vital signs, electrocardiogram [ECG] and laboratory data) will be analyzed according to the following scenario:
 
• For shift table, they will be taken into account in the definition of the worst assessment during study• For description at each timepoint post-baseline, the first available result (in chronological order) per timepoint will be taken into account in the analysis in case of multiple values

	
 For description at baseline, the last available result before first study intervention will be taken into account in the analysis in case of multiple values 
For immunogenicity analysis, unscheduled visits will also be taken into account in the analysis following the same rules as detailed above.
 
For PK analysis, unscheduled samples will not be linked to a scheduled timepoint and will be excluded from summaries.

Moore criteria	
The Moore criteria is defined using the following negative risk factors:
 
 ECOG > 0 at baseline Measurable disease in pelvis if there is presence of target lesions in the pelvis coming from “Disease History” eCRF page Race is “BLACK OR AFRICAN AMERICAN” Disease progression-free interval from date of diagnosis < 1 year. The negative risk is met if the following date is strictly earlier than a year after the date of initial cancer diagnosis coming from “Disease History” eCRF page: 
 The first documented progression disease date from “Prior Anti-Cancer Drug Therapies Details” eCRF page. Date is imputed as the disease history detailed in Section 9.9. Overlapping of prior platinum therapy and exposure to radiotherapy. Platinum-based treatment are defined as treatment with PTs according to a pre-specified WHODrug search list which will be finalized before database lock. If the answer to the question “Was Radiotherapy administered as part of the therapy?” is Yes on the “Prior Anti-Cancer Drug Therapies Details” eCRF page , then it is a negative factor. Dates are imputed as the previous and concomitant medication/procedure detailed in Section 9.9. 
Risk categories are defined as low-risk (0–1 factor met), mid-risk (2–3 factors met), and high-risk (4–5 factors met).

Categorization of participant for COVID-19 impact assessment	
For the assessment of COVID-19 impact on this study, participants will be categorized as being potentially affected by COVID-19 based on the COVID-19 pandemic start date, defined as the minimum of the first COVID-19 death date per country and 11 March 2020 (WHO-start of world-wide pandemic). First death from COVID-19 occurred per country is determined according to the published data

	by European Centre for Disease Prevention and Control (status of 26 th June 2020).
--	---

10 Study Participants

The subsections in this section include specifications for reporting participant disposition and study treatment/study discontinuations. Additionally, procedures for reporting protocol deviations are provided.

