1.3 Schedule of Activities

[figure not shown]
Table 1 Schedule of Assessments

Assessments & Procedures	Screening	Intervention Period (± 3 days)										End-of-Intervention Visit	Safety Follow-up Visit		Long-term Follow-up	Notes
	Day - 28 to First intervention	V1	V2	V3	V4	V5	V6	V7	V8	V9	Until PD	On the Day of or Within 7 Days of Decision to Discontinue	28 Days (± 5 Days) After Last Treatment	12 Weeks (± 2 Weeks) After Last Treatment	Every 12 Weeks (± 2 Weeks)	
		W1	W3	W5	W7	W9	W11	W13	W15	W17						
		D1	D15	D29	D43	D57	D71	D85	D99	D113						
Administrative Procedures																
Written informed consent	X															Screening tests performed as part of routine care prior to informed consent signed will be accepted if they are within 28 day Screening window (see Section 5.4).
Inclusion/exclusion criteria/ Enrollment (if eligible)	X	X														
Demographic data	X															
Medical history	X															See Appendix 2.

Assessments & Procedures	Screening	Intervention Period (± 3 days)										End-of-Intervention Visit	Safety Follow-up Visit		Long-term Follow-up	Notes	
	Day - 28 to First intervention	V1	V2	V3	V4	V5	V6	V7	V8	V9	Until PD	On the Day of or Within 7 Days of Decision to Discontinue	28 Days (± 5 Days) After Last Treatment	12 Weeks (± 2 Weeks) After Last Treatment	Every 12 Weeks (± 2 Weeks)		
		W1	W3	W5	W7	W9	W11	W13	W15	W17							D1
Prior anticancer drug/radiotherapy / procedures for baseline visit	X																Prior anticancer procedures and therapies should at least include prior therapy, prior diagnosis of pre-malignant lesions and treatments, surgical resection and recurrence, and details on anticancer treatments, treatment duration, and treatment responses.
Documentation of concomitant medication and procedures	X	X	X	X	X	X	X	X	X	X	Q2W	X	X				
Documentation of non protocol related hospitalizations, emergency room visits, and outpatient hospital visits		X	X	X	X	X	X	X	X	X	Q2W	X	X	X	X		

Assessments & Procedures	Screening	Intervention Period (± 3 days)										End-of-Intervention Visit	Safety Follow-up Visit		Long-term Follow-up	Notes	
	Day - 28 to First Intervention	V1	V2	V3	V4	V5	V6	V7	V8	V9	Until PD	On the Day of or Within 7 Days of Decision to Discontinue	28 Days (± 5 Days) After Last Treatment	12 Weeks (± 2 Weeks) After Last Treatment	Every 12 Weeks (± 2 Weeks)		
		W1	W3	W5	W7	W9	W11	W13	W15	W17							D1

[figure not shown]
Bintrafusp alfa Drug Administration																	

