11.3 Other Baseline Characteristics

11.3.1 Disease History

Information on disease characteristics collected on the “Disease History” eCRF page will be summarized as follows:

- Tumor histology: Squamous cell carcinoma, Adenocarcinoma, Adenosquamous cell carcinoma, Other
- Time since initial cancer diagnosis (months)
- Time since documented, locally advanced, inoperable or metastatic disease (months)
- Time since last progression of disease prior to study entry (months)
- TNM classification at initial diagnosis: each T, N, M category will be described (TX, T0, N1, etc.)
- MSI status: High, Low, MSS, Unknown. MSI status will be centrally determined by means of the Tumor tissue sample at Baseline and will be provided as external data

This summary table will also be repeated to evaluate subjects split by prior Bevacizumab used or not, and may be repeated for Japanese status (Japanese, non-Japanese, all).

Listing will also be provided with the following information:

- Participant identifier, age, sex, race, tumor histology, date of initial cancer diagnosis (months), date of documented, locally advanced, inoperable or metastatic disease (months), date of last disease progression (months), TNM classification at initial diagnosis and MSI status

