12.4 Previous anticancer treatments and procedures

The previous anticancer treatments and procedures are collected under the “Prior Anti-Cancer Drug Therapies Details” and the “Prior Anti-Cancer Surgeries Details” eCRF pages.

The number of participants in each of the following anticancer treatment categories will be tabulated:

- Participants with at least one type of previous anticancer treatment or procedure (i.e. drug therapy, radiotherapy or surgery)
- Participants with at least one previous anticancer drug therapy
- Participants with at least one radiotherapy
- Participants with at least one previous anticancer surgery
- Participants with at least one previous Concurrent Chemoradiation Therapy (CCRT)

Following details for previous systemic anticancer drug therapy will also be summarized:

- Number of any previous anticancer therapy regimens: 0 / 1 / 2 / 3 / ≥ 4
- Number of prior lines of therapy for metastatic/locally advanced disease: 0 / 1 / 2 / 3 / ≥ 4
- Number of prior lines of therapy for metastatic/locally advanced disease excluding CCRT: 0 / 1 / 2 / 3 / ≥ 4
- Intent of therapy: Neoadjuvant / Adjuvant / Metastatic or Locally advanced

- Best response of last treatment regimen: Complete Response (CR) / Partial Response (PR) / Stable Disease (SD) / Progressive Disease (PD) / Non-Complete Response/Non-Progressive Disease (non-CR/non-PD) / Not Evaluable / Unknown.

Please note that radiotherapies taken alone will not be considered as a line of therapy

Previous anticancer drug therapies and radiotherapies and previous anticancer surgery will be presented in separate listings:

- The previous anticancer drug therapies and radiotherapies listing will contain participant identifier, age, sex, race, regimen ID, PT, medication name, start date, end date, intent of therapy, best response, date of progression. Radiotherapy administered as part of previous drug therapy with start date, end date, total dose, number of fractions and location will also be displayed.
- The previous anticancer surgery listing will contain participant identifier, age, sex, race, date of surgery, name and location of surgery, curative intent of surgery (Y/N), and outcome of surgery.

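### The Moore factor for a progression-free interval under 1 year uses only drug-page progression dates, so an early recurrence after surgery alone can be missed and the risk class can be one level too low

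*SAP*

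**What the plan says.** SAP 9.11 (Other Derivations, Moore criteria) counts five negative factors. For the interval factor it states: "The negative risk is met if the following date is strictly earlier than a year after the date of initial cancer diagnosis". The date that follows is "The first documented progression disease date from" the Prior Anti-Cancer Drug Therapies Details page. No second source or fallback is named. The count then gives low risk (0–1 factors), mid risk (2–3) or high risk (4–5).

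Other places bear on this:

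- **SAP 12.4.** Surgery has its own eCRF page. The listing of prior drug therapies and radiotherapies includes "intent of therapy, best response, date of progression". The prior-surgery listing has "date of surgery, name and location of surgery, curative intent of surgery (Y/N), and outcome of surgery", with no recurrence or progression date.
- **Protocol Table 1 (Section 1.3).** Prior-treatment history is to include "prior diagnosis of pre-malignant lesions and treatments, surgical resection and recurrence".
- **SAP 11.3.1.** The Disease History page supplies the date of locally advanced, inoperable or metastatic disease and the date of last progression before entry. The Moore rule uses neither.
- **Protocol 5.1, criterion 2a(i).** The qualifying platinum may have been given for recurrent disease.
- **SAP 8.2.** Moore class, including an Unknown level, is an efficacy subgroup. The interval factor is also a Yes/No subgroup for ORR and DOR.

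**The concern.** The factor's label is time from diagnosis to first progression. The rule gives that only when the first progression is recorded on the drug-therapy page. Surgery alone, then recurrence, then platinum is an eligible path, and on that path the first recurrence precedes any drug regimen. The rule then picks up a later event.

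Under this mechanism the date used can only be later than the true first recurrence. The factor, and therefore the class, can be too low but not too high. SAP 8.2 describes these subgroups as linked to prognosis. If so, participants with a poorer outlook move into the No interval group or a lower Moore class, and the contrast between groups is blurred.

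**Working it through.** The plan gives no numerical figure to reproduce here. The check has three parts.

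**1. When is the factor missed?** Put diagnosis at month 0, surgery alone, recurrence at month R, platinum start at R + 1, and first drug-page progression at P = R + 1 + D. The values of R and D and the 1-month gap are assumptions. The rule scores the factor as met if P < 12; the true status is R < 12. The factor is missed when R < 12 ≤ P, that is, when D ≥ 11 − R.

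| R | D values tried | P | Missed at |
|---|---|---|---|
| 4 | 2, 3, 4, 6, 9 | 7, 8, 9, 11, 14 | D = 9 |
| 6 | 2, 3, 4, 6, 9 | 9, 10, 11, 13, 16 | D = 6, 9 |
| 8 | 2, 3, 4, 6, 9 | 11, 12, 13, 15, 18 | D = 3, 4, 6, 9 |
| 10 | 2, 3, 4, 6, 9 | 13, 14, 15, 17, 20 | all five |
| 11 | 2, 3, 4, 6, 9 | 14, 15, 16, 18, 21 | all five |

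For example, with R = 8 and D = 4, P = 13 and the factor is not met, although the true interval is 8 months. With R = 4 and D = 3, P = 8 and the factor is still met. The grid shows the mechanism; it gives no frequencies.

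**2. When does the class change?** Let k be the number of the other four factors met. There are 2⁴ = 16 patterns.

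| k | Patterns | Class if missed | Class if counted |
|---|---|---|---|
| 0 | 1 | low | low |
| 1 | 4 | low | mid |
| 2 | 6 | mid | mid |
| 3 | 4 | mid | high |
| 4 | 1 | high | high |

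The class drops in 4 + 4 = 8 of 16 patterns, those with k = 1 or k = 3. These are pattern counts, not probabilities, because the documents give no factor prevalences. The Yes/No interval subgroup is wrong whenever the factor is missed, whatever k is.

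**3. How many participants?** The documents do not give the share treated first by surgery alone, or its early recurrence rate. Assume 10–30% and 30–50%:

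- lower end: 135 × 0.10 × 0.30 = 4.05, about 4
- upper end: 135 × 0.30 × 0.50 = 20.25, about 20

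This counts everyone assumed to recur early after surgery alone. It does not remove those whose drug-page progression also falls under 1 year, whom part 1 shows are scored correctly. So 4 to 20 is a ceiling on missed factors under these assumptions, and class changes would be no more than the missed factors.

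**The case against.** The strongest reply is that the gap is narrow. The drug-therapy page covers neoadjuvant and adjuvant regimens and radiotherapy given with them, so a resected participant who had adjuvant treatment has an entry there. The gap needs surgery without drug therapy, recurrence within 1 year, and a first drug-page progression at 1 year or later. That stands and sets the scope.

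Second, a reader might infer that the true recurrence date is already in the database. The documents do not show this. The surgery listing has no such date, Protocol Table 1 names recurrence as history without saying that a date is recorded, and the Disease History progression date is the last one, not the first. That the drug page records only progression tied to a regimen is also an inference, since the eCRF is not in the documents. SAP 9.9 supports it by referring to response or progression dates in prior treatment.

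Third, counting any date of locally advanced or metastatic disease later than initial diagnosis would score initial staging as progression. Imputing a missing day to the 1st (SAP 9.9) could even create that order within one month. This objection stands against such a rule, and the fix avoids it by requiring a date after surgery.

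Fourth, SAP 6.1 cuts the analyses to an abbreviated report. It keeps the waterfall plot only for selected subgroups without naming Moore class, and the subgroup Kaplan-Meier curves use histology and PD-L1. That narrows the reach but does not remove it, because forest plots by subgroup for ORR, PFS and OS remain on the list.

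**Conclusion.** The point holds in limited form. Followed exactly, SAP 9.11 can score an early recurrence after surgery alone as not meeting the interval factor. The Yes/No subgroup is then wrong, and the Moore class is one level too low if exactly 1 or 3 other factors are met.

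A reader might conclude that every such participant lands in too low a class, or that 4 to 20 participants are misclassified. Neither follows. The first fails in the 8 of 16 patterns where the class is unchanged, and whenever the drug-page date is itself under 1 year. The second treats a ceiling built on assumed shares as an estimate.

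No hypothesis or decision in the available text depends on Moore class, and the primary ORR with its Clopper-Pearson interval is unaffected. This is a minor improvement to subgroup and descriptive outputs. It rests on reading the drug-page date as tied to a drug regimen.

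**What to change.** Keep the drug-page date as the default. For participants whose curative-intent surgery preceded any anticancer drug therapy, define first progression as the earliest of:

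- (a) the first drug-page progression date;
- (b) the Disease History date of locally advanced, inoperable or metastatic disease, only if it falls after the surgery date, so that initial staging is not counted;
- (c) the start date of the first regimen given with metastatic or locally advanced intent after that surgery, taken as the latest possible recurrence date.

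Where these cannot place the recurrence before or after 1 year, including where date imputation decides the order, use the Unknown Moore level already in SAP 8.2, and treat the Yes/No interval subgroup as missing.

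In the timeline above, (c) alone recovers the factor when R + 1 < 12. That covers the missed cases at R = 4, 6, 8 and 10; at R = 11 the regimen starts at month 12, so (b) or Unknown is needed.

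The cost is a short programming change using surgery date and intent, regimen start date and intent, and a Disease History date, all of which the SAP already lists. The downside is that (b) and (c) are proxies: a date soon after surgery could still be a staging result. Field availability should be confirmed against the eCRF. If the change is not made, relabel the factor as first progression recorded on prior drug therapy and state the limitation in the report.
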